Follow-up evaluations will be performed at 6 weeks (± 14 days), 3 months (± 14 days), 6 months (± 30 days) and 12 months (± 30 days) post-surgery. Standard anteroposterior and lateral x-rays of the operated side must be obtained at each follow-up. If the treating surgeon is unable to adequately assess cortical healing due to radiographic obstruction of the implant(s), additional x-ray(s) should be performed. At 3 months a CT scan of the fracture site must be performed in addition. The “Follow-up” set of forms must be completed at each follow-up time point. This includes the assessment of radiologic fracture healing. At 6 weeks, 3, 6 and 12 months, the surgeon must assess the FIX-IT Score and document on the corresponding set of forms. At the 12

month follow-up the “Study Completion” form must be completed additionally. Copies of the original x-ray films and CT scans must be sent to the Sponsor.

Patient Withdrawal

Patient withdrawal has to be documented on the “Study Completion” form. In particular the reason for withdrawal must be documented. The occurrence of any of the following situations gives reason to withdraw a patient from the study:

- Voluntary patient withdrawal. Patients are at liberty to withdraw from the study at any time and for any reason without affecting future treatment.
- Development of a concurrent condition which would interfere with the patient's continued participation.
- Reoperation including complete removal of study device(s).
- Patient is non-compliant.

Lost to Follow-up

Patients will be considered lost to follow-up after they have missed a visit and a reasonable number of attempts to locate and evaluate them have failed. This has to be documented on the “Study Completion” form and in particular the reason should be documented. Patients lost to follow-up will not be replaced within the study.

Minimization of Subjects Lost to Follow-Up

Subject follow-up is extremely important for the conduct of a clinical study. The expectation is to maintain the highest rate of follow-up compliance possible throughout this study. No replacement is foreseen for any patient lost to follow-up. In an effort to minimize lost-to-follow-up subjects, the following recommendations and/or study requirements are essential to ensure proper patient selection and compliance:

1. Patient Eligibility: Subjects will be selected according to the inclusion/exclusion criteria detailed in Section 8 and are expected to return for all follow-up visits.

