- **Severe:** The complication interferes considerably with the subject's usual activities. The event is of definite concern to the subject and/or poses substantial risk to the subject's health or well-being. The event is likely to require medical intervention and/or close follow-up and may be incapacitating or life-threatening. Hospitalization and treatment may be required.

Outcome of Events

The outcome of the event is in relation to the Adverse Event itself, not the treatment rendered (if any) for the event.

- **Resolved:** The outcome of the medical event has been resolved and/or no further treatment is required to treat the reported condition or illness.
- **Tolerated:** The outcome of the medical event will most likely never be resolved. The patient “tolerates” the illness or condition as a matter of life.
- **Pending:** This outcome indicates treatment or diagnostic studies were prescribed for the medical event and the outcome of the medical event is not yet known.
- **Study Withdrawal:** Due to the medical/adverse event, the patient was withdrawn from the study.
- **Device Removal/Reoperation:** The outcome indicates the medical event resulted in the removal of the investigational device or required reoperation of the investigational device.
- **Death:** The outcome indicates the patient death is a direct result of the reported medical/adverse event.

IX. Reporting

The use or disclosure of all protected health information will comply with the HIPAA Privacy Act and Safe Harbor Requirements. All information will be treated with strict adherence to professional standards of confidentiality and will be filed by Zimmer Biomet under adequate security and restricted accessibility by clinical personnel. All reports and communications relating to subjects in the study will identify each patient by the patient’s initials, year of birth, assigned study identification number and date of surgery only.

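### The plan presupposes exits because of an adverse event but sets no later data collection or analysis rule for them, so observed 3-month healing can be too high

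*Combined protocol and SAP*

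**What the plan says.** Four parts of the combined protocol and SAP bear on this.

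- **Section VI, Patient Withdrawal.** The list opens with "The occurrence of any of the following situations gives reason to withdraw a patient from the study". Four situations follow:
  - voluntary withdrawal, which the patient may choose whatever the reason;
  - "Development of a concurrent condition which would interfere with the patient's continued participation";
  - a reoperation in which the study device is taken out completely;
  - non-compliance.

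  The reason must be recorded on the Study Completion form. The list is not stated to be exhaustive, and the concurrent condition is not defined further.
- **Section VI, Recommended Revision Procedure.** After revision surgery the investigator completes an adverse event form and a Study Completion form, and the subject's participation ends. A footnote exempts removal after healing, whether at the patient's request or as standard treatment.
- **Section VIII, Outcome of Events.** Six outcome labels are defined for an adverse event. Study Withdrawal is one: "Due to the medical/adverse event, the patient was withdrawn from the study". Device Removal/Reoperation is another: "The outcome indicates the medical event resulted in the removal of the investigational device or required reoperation of the investigational device".
- **Section VII, Statistical Methods.** Collected data are presented descriptively, with frequencies and percentages for categorical data. No analysis set, denominator or missing-data rule is given.

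The primary endpoint is radiographic and clinical healing at 3 months. Complications are a secondary endpoint, and confirming safety and performance is part of the objective.

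**The concern.** Because Study Withdrawal and Device Removal/Reoperation are separate labels, the first can be used for a subject whose implant is still in place. For that subject the documents give no reason why x-rays, the FIX-IT score and complication reports should stop. The device is implanted once, and Section VIII says participation is not expected to affect medical treatment.

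A subject who leaves because of a complication is plausibly less likely than the others to be healed at 3 months and more likely to have a further event. If such subjects drop out of the denominator, the loss is informative and the healing percentage tends to rise. The study is non-controlled, so no second arm would reveal the shift. Later complications in these subjects would also go unseen, which matters for a study meant to confirm safety.

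**Working it through.** **The plan's own figure.** Section VII expects 5 patients per site at 8 sites: 5 × 8 = 40, which reproduces. Section V continues enrolment to 30 if fewer are enrolled after one year. The range is therefore N = 30 to 40. The plan gives no power calculation, withdrawal rate or expected healing rate.

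**The sections side by side.**

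| Question | Section VI, Patient Withdrawal | Section VI, Recommended Revision Procedure | Section VIII, Outcome of Events |
|---|---|---|---|
| Can an adverse event lead to exit? | Not named as such; possible through voluntary withdrawal, an interfering concurrent condition or complete removal | Yes, after revision | Presupposed by a separate label |
| Is the reason or event recorded? | Yes | Yes | Yes |
| Are healing or complication data collected after exit? | Not provided for | Not provided for | Not provided for |

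Section IX requires complication outcomes to be updated during the study, but does not extend this to subjects who have left.

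**Size of the possible bias.** Let N be the number enrolled, w the number who leave after an adverse event before the 3-month visit, and h the number healed among the N − w observed.

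- Observed-case percentage: h/(N − w)
- All enrolled, none of the w healed: h/N
- All enrolled, all of the w healed: (h + w)/N
- Worst-case overstatement: h/(N − w) − h/N

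Assumed, because the documents give neither: w = 2 or 4, and about 90% healed among those observed.

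| N | w | Observed | None of w healed | All of w healed | Worst-case overstatement |
|---|---|---|---|---|---|
| 40 | 2 | 34/38 = 89.5% | 34/40 = 85.0% | 36/40 = 90.0% | 4.5 points |
| 40 | 4 | 32/36 = 88.9% | 32/40 = 80.0% | 36/40 = 90.0% | 8.9 points |
| 30 | 2 | 25/28 = 89.3% | 25/30 = 83.3% | 27/30 = 90.0% | 6.0 points |
| 30 | 4 | 23/26 = 88.5% | 23/30 = 76.7% | 27/30 = 90.0% | 11.8 points |

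The possible error is lopsided. With N = 40 and w = 4 the observed figure can be 8.9 points too high but only 90.0 − 88.9 = 1.1 points too low.

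**Sensitivity to the assumptions.** With about 80% healing among those observed, the worst case runs from 30/38 = 78.9% against 30/40 = 75.0% (about 4 points; N = 40, w = 2) to 19/24 = 79.2% against 19/30 = 63.3% (about 16 points; N = 30, w = 6).

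**Precision for later complications.** If no later event is seen in n subjects, the one-sided 95% upper bound is 1 − 0.05^(1/n). This is 7.2% for n = 40 and 8.4% for n = 34. Losing six subjects costs little precision; the main problem is bias.

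**The case against.** The strongest reply is that Outcome of Events is a coding list. It records what happened and authorises nothing. A reader might infer that it creates a withdrawal rule in conflict with Patient Withdrawal. The documents do not support that: the withdrawal list is not stated to be exhaustive, a subject may leave voluntarily for any reason, and complete removal is listed. A subject who chooses to leave because of a complication fits both sections. The concurrent-condition ground also requires interference with continued participation, so a complication that leaves the subject able to attend does not plainly meet it. All of this stands.

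A reader might also infer that the complication behind the exit is lost, or that each missed second event lowers the overall complication rate by one subject's share. Neither follows. Section VIII requires every adverse event to be reported, Section IX puts it on the Complication form, and the withdrawal reason is documented. A subject with one recorded event already counts in the proportion with any complication, so a missed second event does not change that proportion. It could change the rate of a specific complication type.

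Finally, the missing denominator rule affects every kind of loss, including loss to follow-up and non-compliance. That is true, but exits caused by adverse events are the ones most likely to be related to healing, and the plan itself anticipates them.

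**Conclusion.** The point holds as a gap in follow-up and analysis, not as a flat contradiction between sections. The plan anticipates exits because of an adverse event, does not say consistently when a complication ends participation, collects nothing afterwards, and has no rule for counting these subjects.

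At N = 40 with about 90% healing in the rest, observed 3-month healing could be too high by about 4.5 points with 2 exits and about 9 points with 4. These are worst cases. They assume that every exit falls before the 3-month visit, that none of those subjects heals, and that the percentage is taken over observed subjects, which is the natural reading of Section VII but is not stated there. The exit counts and the healing rate are assumptions. The change is worth making because it is cheap and removes an avoidable bias.

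**What to change.** 1. Reconcile Patient Withdrawal, Recommended Revision Procedure and Outcome of Events on when a complication ends participation.
2. State that an adverse event or concurrent condition does not by itself end scheduled data collection in a subject who still consents and can be assessed. This concerns observation only. It leaves clinical care and the right to withdraw untouched.
3. In Section VII, report 3-month healing over all enrolled subjects, with those who left after an adverse event counted as not healed, beside the observed-case percentage. Give both numerators and denominators.
4. Optionally, remove Study Withdrawal from the event outcomes, since the Study Completion form already records the reason for leaving. Keeping it does no harm once items 1 to 3 are in place, and it links the event to the exit.

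The cost is protocol wording, one extra line in the healing table, and a few visits that are already on the schedule. The reported healing rate may be less favourable.

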Appendix A: Case Report Forms

Appendix B: Patient Information and Patient Consent
